16.2 Sample Size Justification and Randomization

Subjects will be randomized in a 1:1 allocation ratio using a permuted block design with stratification based on the clinical center and atrial fibrillation status. We plan to randomize 400 subjects with planned follow-up of 26 weeks. The primary efficacy endpoint is the proportional change from baseline in the AUC for NT-proBNP levels measured at 2, 4, 8, 12 and 24 weeks.

Based on recent Heart Failure Clinical Research Network (HFN) trials with similar follow-up requirements, we are anticipating a dropout / withdrawal of consent rate of approximately 5%. However, due to deaths and other sample collection issues we anticipate as many as 20-25% of subjects will not have NT-proBNP data at the week 24 assessment.

For the primary analysis, the AUC data will be log transformed and subjects missing the NT-proBNP data at the week 24 assessment will be assigned the last observation carried forward (LOCF). Based on a 2-sample t-test with type I error of 0.05 two-sided, the total sample size of 400 randomized subjects will provide 80% and 90% power to detect a differences of 19% and 21% for LCZ696 compared to valsartan. The PARAMOUNT phase II clinical trial observed a 23% greater reduction in NT-proBNP for LCZ696 compared to valsartan at 12 weeks post-randomization in patient population with HFpEF. ⁶ The HF Network investigators believe a 20% reduction in NT-proBNP would be considered a clinically significant improvement, and this level of change falls within a range considered clinically meaningful in a recent comparative effectiveness review published by AHRQ. ⁷

Sensitivity analyses will examine the influence of the imputation for the informatively missing data. For the complete case analysis, the total sample size of 400 subjects will provide approximately 80% and 95% power to detect reductions of 20% and 25% for LCZ696 compared to valsartan, respectively. These calculations were based on a two-sample t-test and assume that the standard deviation of the log-transformed 180-day AUC measure is 0.70. ⁸

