Another secondary analysis of the AUC data for NT-proBNP will be conducted using a Wilcoxon nonparametric test with a worst-rank imputation based on the time-to-death. ⁹ A sample size of 190 subjects per group with available data will provide 80% power to detect the probability of 0.58 that an LCZ696 subject will have a better response than a valsartan subject. Similarly the sample size will provide 90% power to detect the probability of 0.60 that an LCZ696 subject will have a better response than a valsartan subject.

For the composite endpoint of all-cause mortality or first HF re-admission, we anticipate a 40% event rate at 24-weeks in the valsartan arm. The total sample size of 400 subjects will provide approximately 88% power to detect a difference of 40% vs. 25% for the LCZ696 arm. Similarly, there will be 55% power to detect a difference of 40% vs. 30%. The calculations were performed

using nQuery 7.0 and assume a 0.05 type I error rate (two-sided) with 1:1 randomization.

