### 2.2 Randomization

Patients are randomized in a 1:1 ratio to either LCZ696 + Valsartan-placebo or Valsartan + LCZ696-placebo. The randomization scheme consists of a permuted block design with stratification by clinical site and atrial fibrillation status.

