[Note: The sensitivity analysis using imputation of 2.5xBaseline value will not be performed due to the concern that the impact of missing data due to the COVID-19 pandemic might overstate the effect of the imputation.]

- 3) For patients missing Week 24 value, impute 5xBaseline value for Week 24

[Note: This sensitivity analysis using imputation of 5xBaseline value will not be performed due to the concern that the impact of missing data due to the COVID-19 pandemic might overstate the effect of the imputation.]

- 4) For patients that receive a left ventricular assist device (LVAD) or heart transplant prior to the Week 24 assessment, remove all NT Pro BNP results post-procedure due to the potential for an artificial response due to the procedural impacts on the heart. Missing values will be imputed in the same fashion as in the primary analysis.
- 5) To address a potential question seen in some journal reviews, the primary model will be run again, adding a new covariate for the effect of enrolling site.
- 6) Wilcoxon with worst rank imputation based on time to death and then ranking worst to best NT Pro BNP AUC for those patients that did not die prior to 24 week visit
- 7) Re-calculate the primary endpoint analysis and the remaining sensitivity analyses using the original ITT population.

Statistical Tests: For the Primary and Sensitivity Analyses 1 – 5, a mixed model (PROC MIXED in SAS) will be used to test the significance of differences in the area under the curve for the Log(NT Pro BNP AUC) between the two treatment arms.

For Sensitivity Analysis 6, a Wilcoxon test (PROC NPAR1WAY in SAS) will be used to test whether there is a difference in the distribution of ranks between the two treatment arms.

Interpretation of Results: A lower value for the AUC indicates an improvement in the LCX696 arm versus the Valsartan arm. Lower rank scores indicate worse outcomes in the worst rank analysis.

---

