## 12. Exploratory Endpoint Descriptions

### 12.1 – Exploratory Endpoint #1

Endpoint Description: A four level modified clinical composite endpoint including 1) death, 2) LVAD or Heart Transplant (including listing status of 1A, 1B or 1-4), 3) multiple HF hospital admissions, and 4) single HF admission, using the pre-COVID-19 population.

Response Variable Definition: The unmatched approach to the win ratio of Pocock will be used. In general terms, each patient will be placed into one of the hierarchical groups based on the comparison of LCZ696 versus Valsartan patients. The hierarchy for the comparisons is as follows:

- (a) LCZ696 patient had death first
- (b) Valsartan patient had death first
- (c) LCZ696 patient had LVAD or HTP first
- (d) Valsartan patient had LVAD or HTP first
- (e) LCZ696 patient had multiple HF hospital admissions first
- (f) Valsartan patient had multiple HF hospital admissions first
- (g) LCZ696 patient had single HF hospital admission first
- (h) Valsartan patient had single HF hospital admission first
- (i) None of the above

Additional Covariates in Addition to Randomized Treatment: None

Handling of Dropouts and Missing Data: All patients are expected to have some data to address this endpoint. No further adjustments for incomplete or missing data will be made.

Sensitivity Analysis: Re-calculate the endpoint analysis using the original ITT population.

Statistical Tests: The win ratio approach of Pocock will be used to evaluate each endpoint. Calculation of the test statistics, p-values and confidence intervals is detailed in the Pocock manuscript (Pocock SJ, Ariti CA, Collier TJ, Wang D. The win ratio: A new approach to the analysis of composite endpoints in clinical trials based on clinical priorities. *Eur Heart J*.33:176-182).

Interpretation of Results: A win ratio of 1.0 is the null value. Estimates below 1.0 indicate a worse outcome and win ratios greater than 1.0 indicate a favorable effect for the LCZ696 arm.

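### Sensitivity Analysis 6 and the exploratory win ratio leave out the atrial fibrillation stratum that every primary, secondary and tertiary model in the SAP adjusts for, at a small cost in precision

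*SAP*

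**What the plan says.** SAP 2.2 describes a "permuted block design with stratification by clinical site and atrial fibrillation status". Protocol 10.8 and 16.2 name the same two factors.

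AF is a covariate in the primary model (SAP 9.1), in all five secondary endpoints (SAP 10.1 to 10.5) and in all thirteen tertiary endpoints (SAP 11.1 to 11.13).

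Two comparisons of outcome depart from this:

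- **Sensitivity Analysis 6 (SAP 9.1).** Deaths before the 24-week visit are ranked worst by time of death, and survivors are then ranked by NT-proBNP AUC. For this analysis, "a Wilcoxon test (PROC NPAR1WAY in SAS) will be used to test whether there is a difference in the distribution of ranks" between the arms. No stratum or covariate is named. Protocol 16.4 names none either.
- **Exploratory win ratio (SAP 12.1).** The unmatched form is used, and the entry reads "Additional Covariates in Addition to Randomized Treatment: None". Protocol 16.5 also specifies the unmatched form.

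Neither document gives a reason for leaving AF out.

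**The concern.** When allocation is balanced within AF strata and AF predicts the outcome, a test that ignores the strata counts between-stratum variation as noise. Its standard error is then too large, so the test tends to be conservative and loses some power.

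This deserves a line because Sensitivity Analysis 6, with its re-run in the original ITT population, is the only retained NT-proBNP analysis that ranks death as the worst result. The imputations at 2.5 and 5 times baseline have been withdrawn (SAP 9.1), and the primary analysis carries the last value forward. Protocol 16.2 expects up to 20 to 25% of subjects to lack a week-24 value, partly because of deaths. If Sensitivity Analysis 6 differs from the primary result, the reader will want to know whether deaths explain it. As planned, the AF adjustment disappears at the same step.

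**Working it through.** **1. The plan's own power figure.** Protocol 16.2 states: "A sample size of 190 subjects per group with available data will provide 80% power to detect the probability of 0.58", and "Similarly the sample size will provide 90% power to detect the probability of 0.60". The Noether formula for an unstratified 1:1 Wilcoxon test is

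power = Φ(√(6n) × (P − 0.5) − 1.96), with n per arm.

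At n = 190, √(6 × 190) = 33.76.

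- P = 0.58: 33.76 × 0.08 − 1.96 = 0.74, giving 77.1%.
- P = 0.60: 33.76 × 0.10 − 1.96 = 1.42, giving 92.2%.
- Solving for P: 0.5 + (1.960 + 0.842)/33.76 = 0.583 for 80%, and 0.5 + (1.960 + 1.282)/33.76 = 0.596 for 90%.

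The stated figures therefore reproduce once P is rounded to two decimals. They come from an unstratified calculation.

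**2. Current size.** SAP 3 analyses 335 patients, about 167.5 per arm. √(6 × 167.5) = 31.70, and 31.70 × 0.083 − 1.96 = 0.67, so power at P = 0.583 is about 75% rather than 80%. This loss is unrelated to AF, but it leaves less precision to spare.

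**3. Worst-rank Wilcoxon, with and without the AF stratum.**

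- *From the documents:* 335 patients (SAP 3); about 40 centres (Protocol 11.2); 1:1 allocation in blocks within site and AF; "standard deviation of the log-transformed 180-day AUC measure is 0.70" (Protocol 16.2); and a 20% reduction, −ln(0.80) = 0.223 on the log scale.
- *Assumed:* block size 4; 15% deaths among control patients without AF; a treatment risk ratio for death of 0.9; and the AF values in the table.
- *Unstratified test:* z = (W − E[W])/√V over all patients.
- *Van Elteren test:* z = Σ w(W − E[W])/√(Σ w²V) over the two AF strata, with w = 1/(stratum size + 1).

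There were 2,000 simulated trials for type I error (Monte Carlo SE about 0.005) and 1,000 for power (SE about 1.6 points).

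| AF prevalence; shift in log AUC; AF risk ratio for death | Type I error: unstratified vs stratified | Power: unstratified vs stratified | Gain (points) |
|---|---|---|---|
| 30%; 0; 1.0 | 0.047 vs 0.046 | 64.3% vs 64.2% | −0.1 |
| 30%; 0.2; 1.3 | 0.049 vs 0.050 | 60.7% vs 60.7% | 0 |
| 40%; 0.4; 1.5 | 0.042 vs 0.043 | 57.5% vs 59.9% | 2.4 |
| 50%; 0.7; 2.0 | 0.038 vs 0.050 | 48.4% vs 57.1% | 8.7 |

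The last row assumes a shift of one full SD (0.7/0.70) and doubled mortality in AF patients. The gains in the first three rows are near simulation error.

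A run of the third row with between-site variation added (SD 0.3) gave type I error of 0.035 vs 0.036 and power of 51.2% vs 53.9%. AF stratification therefore does not remove conservatism that comes from site.

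**4. A second set of assumptions.** These were 35% AF, 12% control deaths, a 20% reduction and a death hazard ratio of 0.8, with 3,000 trials per cell. A shift of 0.5 SD gave 71.9 to 73.3% unstratified against 73.7 to 75.0% stratified, a gain of about 1.5 to 2.5 points. A shift of 0.3 SD gave 0 to 0.6 points, and no shift gave no loss.

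**5. Win ratio.** This used 1,500 trials per cell, an assumed treatment hazard ratio of 0.65 for events and a permutation variance. With an AF hazard ratio of 1.5, power was 72.6% against 73.4% (0.8 points). With 2.0 it was 74.8% against 76.7% (1.9 points).

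**6. Pairs lost by within-stratum pairing.** At an assumed 35% AF, the share of pairs that mix AF and non-AF patients is 2 × 0.35 × 0.65 = 0.455, about 45%.

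**The case against.** Much of the opposing case stands.

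- **Importance.** One analysis is a sensitivity analysis and the other exploratory. A reader might take them for main comparisons, but the documents do not label them so, and no decision rule rests on either.
- **Uniqueness.** A reader might infer that these are the only comparisons without AF. The serious adverse event comparison (SAP 13.1) also has no covariates. Site, the other stratification factor, enters only Sensitivity Analysis 5.
- **Validity.** A reader might conclude that the patients are not analysed as randomised. They are compared by assigned arm under intention to treat. An unstratified test after stratified allocation is valid, and step 3 shows no inflation of type I error.
- **Evidence that AF matters.** Protocol 16.4 mentions outliers from clinical changes, AF status among them. That reads most naturally as change during follow-up. It does not show that baseline AF shifts an outcome expressed as a ratio to each patient's own baseline.
- **Comparability.** Stratifying by AF does not put Sensitivity Analysis 6 on equal terms with the primary model, which also adjusts for baseline log NT-proBNP.
- **Fidelity to the protocol.** Protocol 16.4 and 16.5 specify the unstratified Wilcoxon and the unmatched win ratio, and the SAP follows them. This argues for adding the stratified forms while keeping the others. It does not argue against stratifying.
- **Partial cover elsewhere.** SAP 15 plans selected analyses by AF status. The key secondary endpoint counts days after death as event days and lists AF. Neither gives an AF-stratified worst-rank test or win ratio.

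The omission of site does not excuse the omission of AF. With 335 patients at about 40 centres there are roughly 8 per site (335/40), whereas AF gives two strata that the SAP already uses in its models.

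**Conclusion.** The point holds as a small matter of precision and consistency. Sensitivity Analysis 6 and the win ratio set aside a stratum that the trial randomises by and that every primary, secondary and tertiary model uses. The result is neither bias nor a false-positive risk: unstratified type I error was 0.038 to 0.049 across the four AF scenarios.

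The cost depends on AF prevalence and on how strongly AF relates to the ranked outcome, and the documents give neither. Under the assumed values, worst-rank power falls by about 0 with no or weak AF effect and by about 1.5 to 2.5 points with a moderate effect. A loss near 9 points needs the most extreme scenario. For the win ratio the loss was 0.8 to 1.9 points under one set of assumptions. No scenario showed a material loss from stratifying.

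**What to change.** - **SAP 9.1, Sensitivity Analysis 6:** specify the van Elteren test with AF status at randomisation as the stratum, for example PROC FREQ with the CMH option and modified ridit scores.
- **SAP 12.1:** add a win ratio in which pairs are formed within AF strata and combined with stated weights, for example stratum-size weights.
- **Both:** keep the protocol-specified unstratified versions alongside. If treatment codes are already open, label the stratified versions supplementary.
- **Alternatively:** state why AF is left out of these two analyses.

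The cost is a few lines of SAP text and a little extra programming, with no new data. The stratified win ratio estimates a within-stratum quantity from fewer pairs, and the SAP should say so. The stratified Wilcoxon should not be described as fully matching the primary model.

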## 10. Secondary Endpoint Descriptions

### 10.1 – Secondary Endpoint #1

Endpoint Description: Days alive and out of hospital at 24 weeks, not listed for transplant (Status 1A, 1B or 1-4) or undergoing transplant, implanted with an LVAD, maintained or started on continuous inotropic therapy for  $\geq 7$  days, or has had two hospital admissions for heart failure (HF), other than the index admission. The days alive and out of hospital will end on the day of the second HF readmission, if applicable, using the pre-COVID-19 population.

Response Variable Definition: Each component of the endpoint will have daily flags created indicating whether the patient met the endpoint on that specific day. Days will start at day of randomization (Day 0) and continue until a maximum of 163 (beginning of 24 week visit window). Determination of the final evaluable date will depend upon which component is under evaluation. Any data collected after 163 days post randomization will not count for this endpoint.

Days alive: If a patient died between randomization and 163 days post randomization, each day will be coded as a 0 if they were alive and will be coded as a 1 if the patient has previously died. All 163 post-randomization days will be evaluable if the patient died. If the patient had not died, the last evaluable date will be minimum of 163 days post randomization, date of Week 24 visit, date of withdrawn consent or date of loss to follow-up.

Out of hospital: If a patient was randomized while admitted to the hospital, each day the patient was in the hospital from randomization to discharge will be coded as a 1, otherwise the coded value will be a 0. For every other unplanned hospital admission, the patient will be coded as a 0 if they were not hospitalized and coded as a 1 if they were, using the admission and discharge dates as the anchors. The last evaluable date will be minimum of 163 days post randomization, date of Week 24 visit, date of withdrawn consent, date of death or date of loss to follow-up.

Not listed for transplant or undergoing transplant: If a patient either has been listed for heart transplant or received a transplant, each day will be coded as a 0 if they were not listed/transplanted and will be coded as a 1 if the patient had been listed or transplanted. The last evaluable date will be minimum of 163 days post randomization, date of Week 24 visit, date of withdrawn consent, date of death or date of loss to follow-up.

Not implanted with a LVAD: If a patient had been implanted with a LVAD, each day will be coded as a 0 if they were not implanted and will be coded as a 1 if the patient had been implanted. The last evaluable date will be minimum of 163 days post randomization, date of Week 24 visit, date of withdrawn consent, date of death or date of loss to follow-up.

Not maintained or starting continuous IV inotropes for at least 7 days: If the patient had been taking continuous IV inotropes for at least 7 days, each day from the start of inotropes (or randomization date if inotropes started prior to randomization) through the discontinuation of inotropes will be coded as a 1. If the patient does not have a discontinuation date, the assumption will be that inotropes continued to minimum of 163 days post randomization, date of Week 24 visit, date of withdrawn

consent, date of death, or date of loss to follow-up. For those days where the patient is not taking inotropes, the coded value will be 0.

Free of two heart failure hospitalizations: If the patient had two unplanned heart failure hospitalizations, each day from the second HF admission will be coded as a 1. Every day prior to the second HF admission will be coded as a 0. Coding will continue through a minimum of 163 days post randomization, date of Week 24 visit, date of withdrawn consent, date of death, or date of loss to follow-up.

Composite endpoint of event free days: Using each of the endpoint components above, determine the maximum value for the coded value for each of Day 0 through 163. If no endpoints met, the patient met the criteria for an event free day.

Additional Covariates in Addition to Randomized Treatment: atrial fibrillation status at time of randomization

Handling of Dropouts and Missing Data: To account for missing data due to right censoring, inverse probability weighted estimates will be calculated for each treatment group. These estimators adjust for the potential bias due to administratively censored data by reweighting the observed data by a function of the Kaplan-Meier estimate of the censoring distribution. The data will be partitioned from randomization (Day 0) to Day 79 and Day 80 to Day 163.

Sensitivity Analyses:

- 1) Instead of using the beginning of the Week 12 visit window (79 days post-randomization) and Week 24 visit window (163 days post-randomization) to count event days, use the projected Weeks 12 and 24 visit dates (84 and 168 days post randomization, respectively), using the pre-COVID-19 population.
- 2) Re-calculate the endpoint analysis using the original ITT population.
- 3) Re-calculate sensitivity analysis 1) using the original ITT population.

Statistical Tests: The Kaplan-Meier estimator for the censoring distribution will be obtained by reversing the usual role of survival and censoring within PROC LIFETEST. A partitioned version of the Bang-Tsiatis estimator will be applied using PROC GENMOD in SAS. The IPW estimate using partitions at Days 79 and 163 will be used to estimate the difference between treatment groups.

Interpretation of Treatment Comparison: A lower number of days affected by the components of this composite endpoint (higher number of event free days) indicates that LCZ696 provides an improved clinical response versus Valsartan.

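### Key secondary day count (SAP 10.1): inotrope use at entry is counted but not adjusted for, and the last-evaluable-date rules omit the 1 March 2020 cut; both are small and cheap to fix

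*SAP*

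**What the plan says.** SAP 10.1 builds the endpoint from daily flags over Day 0 to Day 163. A day is event-free if no component flag is 1.

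**States present at entry.** A qualifying inotrope course is flagged from its start ("or randomization date if inotropes started prior to randomization) through the discontinuation of inotropes will be coded as a 1"). After it stops, the flag is lifted: "For those days where the patient is not taking inotropes, the coded value will be 0". An index hospital stay is flagged from randomisation to discharge. For transplant listing, days are "coded as a 0 if they were not listed/transplanted and will be coded as a 1 if the patient had been listed or transplanted", with no statement on listings made before randomisation. Protocol 9.2 accepts current inotropic therapy as a qualifying finding. Protocol 9.3 excludes listed patients only if they are also in hospital. Protocol 13.2 counts inotropes that are maintained as well as those newly started.

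**Model.** "Additional Covariates in Addition to Randomized Treatment: atrial fibrillation status at time of randomization". Protocol 16.5 specifies the same model and calls this the key secondary endpoint.

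**Dates.** For the days-alive component, "If the patient had not died, the last evaluable date will be minimum of 163 days post randomization, date of Week 24 visit", withdrawal or loss to follow-up. The other components add death. For inotropes, "If the patient does not have a discontinuation date, the assumption will be that inotropes continued to minimum of 163 days post randomization" or the earliest of the same dates. None of these lists contains 1 March 2020. SAP 3, however, excludes data collected after that date for the pre-COVID-19 population, which 10.1 uses. It says 25 of the 335 patients lose some visit information.

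**Censoring.** Inverse probability weighting is applied: "These estimators adjust for the potential bias due to administratively censored data". "The data will be partitioned from randomization (Day 0) to Day 79 and Day 80 to Day 163".

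**The concern.** There are two separate matters.

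First, a patient who enters on continuous inotropes begins with event days whichever arm is assigned. That spread is predictable before randomisation, yet the model leaves it in the residual. The SAP does otherwise elsewhere: 9.1 adjusts the primary endpoint for baseline log NT-proBNP, and 11.12 adjusts KCCQ for its baseline score. The stake is the width of the confidence interval, plus exposure to chance imbalance.

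Second, a programmer who follows 10.1 line by line would delete the data after 1 March 2020 but keep the days. New events after the cut would become event-free days. Listing, LVAD and second-HF-admission flags already set would stay at 1. An inotrope course with no stop date would run on as 1 to Day 163. The Kaplan-Meier estimate of the censoring distribution would treat these patients as fully followed.

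**Working it through.** **Plan's own dates.** 7 December 2019 + 84 days = 29 February 2020, the last day before the cut, so the entry limit in SAP 3 reproduces. So do 365 - 335 = 30 patients left out, 84 - 5 = 79 and 168 - 5 = 163. The plan states no power, mean or SD for this endpoint.

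**Part 1: precision.** Assumptions, none from the documents: a share p = 5% is on inotropes at entry; other patients have mean M event-free days and SD S, with (M, S) = (120, 45) or (110, 55). N = 335 (SAP 3), allocated 1:1. In case A, flagged patients have no event-free days. In case B, their courses later stop, giving mean 60 and SD 50.

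- Between-group variance, removable by adjustment: p(1-p)(M - m)², where m = 0 (A) or 60 (B).
- Within-group variance: (1-p)S² (A) or (1-p)S² + p × 50² (B).
- 95% CI half-width: 1.96 × sqrt(variance × 4/335).

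| Case | M, S | Between | Within | Share removed | Half-width (days), unadjusted to adjusted |
|---|---|---|---|---|---|
| A | 120, 45 | 684.0 | 1,923.75 | 26.2% | 10.9 to 9.4 |
| A | 110, 55 | 574.75 | 2,873.75 | 16.7% | 12.6 to 11.5 |
| B | 120, 45 | 171.0 | 2,048.75 | 7.7% | 10.1 to 9.7 |
| B | 110, 55 | 118.75 | 2,998.75 | 3.8% | 12.0 to 11.7 |

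At p = 1% the shares are 3.8-6.6% (A) and 0.8-1.7% (B), and the half-width narrows by less than half a day. At p = 10% they are 28.6-41.6% and 7.0-13.5%. If half the zero-day patients were listings not recorded at baseline, the case A share at 5% would fall to 8.1-12.8%.

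**Part 2: the cut.**

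1. 1 March 2020 is Day 85 for an entrant of 7 December 2019 and Day 163 for one of 20 September 2019. Entrants from 21 September to 7 December therefore lose between 1 and 163 - 85 = 78 days. Over these 78 entry dates the mean loss is (1 + 78)/2 = 39.5 days. Every lost day lies in the Day 80-163 partition.
2. Patients affected: at most 25 (SAP 3). Some of those may lose only a visit after Day 163. The 26-week call can fall as late as Day 182 + 3 = 185, so entrants from 29 August (101 entry dates) could be among the 25. Assuming even entry, 25 × 78/101 = 19.3. That is 5.8-7.5% of 335.
3. Person-days in the partition: 19.3 × 39.5/(335 × 84) = 2.7%, and 25 × 39.5/(335 × 84) = 3.5%.
4. If the cut were treated as censoring, the weight at Day 163 would rise by about 1/(1 - 0.058) = 1.06 to 1/(1 - 0.075) = 1.08.
5. Overcount of event-free days, assuming an overall mean of 110-120 out of 164. If every event is permanent with constant hazard, about 2.6-2.9 days per truncated patient. If every event day is transient, 39.5 × (164 - 120)/164 = 10.6 to 39.5 × (164 - 110)/164 = 13.0. Averaged over 335 patients, this runs from 2.6 × 19.3/335 = 0.15 to 13.0 × 25/335 = 0.97 days. Inotrope carry-forward works in the opposite direction.
6. In sensitivity analysis 1 (Day 168) the affected entrants are those from 16 September, with up to 168 - 85 = 83 days lost.

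**The case against.** On the covariate: protocol and SAP agree on the AF-only model, AF is a stratification factor, and leaving out an optional prognostic covariate is not an error. The large gains arise only if flagged patients never have an event-free day. Where courses stop, the interval at 5% prevalence narrows by only 0.2-0.4 day. The calculation is a plain two-sample comparison; the variance of the planned partitioned Bang-Tsiatis estimator was not modelled. A change of main model would also follow an interim analysis that computed conditional power for secondary endpoints (SAP 14). All of this stands. It limits the point to a cheap gain in precision and dictates how the change should be made.

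A reader might infer that counting inotropes from Day 0 biases the comparison or departs from the protocol. It does neither: the state precedes randomisation, and the protocol's definition covers maintained therapy. A reader might also infer that outpatients listed before entry are flagged every day. That is one literal reading; the text can equally mean listing during follow-up. Listing is also not among the Visit 0 items in protocol 12.1, so a covariate may not exist.

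On the cut: SAP 3 applies it to this population, the weighting text refers to administrative censoring, and the Day 79 partition precedes the earliest possible cut at Day 85. Read together, these suggest that censoring was intended, and this stands too. What is missing is the rule that gives the date, and the explicit minimums in 10.1 point the other way. The re-analyses in all randomised patients are a partial check, since they also add 30 patients and the pandemic-period data.

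**Conclusion.** The point holds as two small weaknesses.

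The first concerns precision, not bias. Its size rests wholly on assumed prevalence, mean and SD: at 5% prevalence, 4-8% of variance if courses later stop and 17-26% if flagged patients have no event-free days; near 1% it is trivial. A claim of serious lost power would go beyond the documents, which give neither a power for this endpoint nor the share of patients on inotropes at entry.

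The second is a missing censoring date. Read literally, 10.1 treats about 19 to 25 of 335 patients as followed to Day 163 when they are not, and leaves them out of the censoring weights. A reader might infer a distorted treatment effect. The documents do not support that: the expected shift in the mean is about 0.15-1.0 day under the assumptions above, it falls in both arms, and nothing indicates a difference between them. It is a minor correction that writes down what SAP 3 and the weighting text appear to intend.

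**What to change.** Make both changes to SAP 10.1 as a dated amendment.

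1. Keep the endpoint definition and AF. If the analysis is still blinded, add continuous-inotrope use at randomisation to the weighted regression, justify it on pre-randomisation grounds only, and report the AF-only model as a sensitivity analysis. If unblinding has happened, keep AF-only as the main model and report the adjusted model as the sensitivity analysis; protocol 16.1 requires analyses to be defined before unblinding. Inpatient status at randomisation is the same kind of explicit carry-over and could be treated alike. Use baseline listing only if it was recorded.
2. For the pre-COVID-19 analyses only (the main analysis and sensitivity analysis 1), add 1 March 2020 to each last-evaluable-date minimum and to the inotrope carry-forward minimum. Treat it as administrative censoring in the Kaplan-Meier weights for patients not known to have died before it. Leave the re-analyses in all randomised patients unchanged.
3. State how a listing made before randomisation is coded, and whether 1 March itself is kept; SAP 3 is inconsistent by one day on this.

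The cost is SAP wording, one or two covariates and a date in the program. Inotrope dates are already needed for the daily flags, and medications are reviewed at Visit 0, so no new data are required.
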